6.8 Rationale for trial population

The target population for this trial is insulin naïve subjects with T2DM inadequately controlled on SGLT2i treatment \pm OAD treatment. The following types of anti-diabetic pre-trial therapy are allowed: SGLT2i monotherapy or SGLT2i in combination with metformin ± DPP4i ± pioglitazone for a period of at least 90 days prior to screening (inclusion criteria 7). Since pioglitazone should not be combined with dapagliflozin this is specified in the inclusion criteria. Subjects on DPP4i should discontinue this OAD treatment at randomisation. Thus the randomised subjects will be on either SGLT2i monotherapy or SGLT2i ± metformin ± pioglitazone, this treatment should be unchanged throughout the trial, unless there is a safety concern.

To ensure a homogeneous SGLT2i-treated population, subjects may not be treated with other antidiabetic treatment (e.g., other OADs [such as sulfonylureas], or GLP-1 receptor agonists) within 90 days of screening (exclusion criteria 4 and 5). Stable OAD treatment for at least 90 days prior to enrolment is furthermore chosen to minimize carry over effect of OAD treatment on trial endpoints,

Protocol	CONFIDENTIAL	Date:	20 November 2015	Novo Nordisk
Trial ID: NN9068-4229		Version:	2.0	
UTN: U1111-1168-9343		Status:	Final	
EudraCT No.: 2015-001596-48		Page:	28 of 107	

including weight loss secondary to initiation of SGLT2i treatment, and to ensure a population tolerating SGLT2i treatment.

To ensure the safety of the subjects, subjects that are particularly vulnerable due to various illnesses are excluded from participation.

Eligible subjects are presenting with an HbA_{1c} in the range of 7.0-11.0% (both inclusive), while maintaining antidiabetic treatment with SGLT2i as described above. This HbA_{1c} range is chosen to include a representative T2DM population in need of further intensification without imposing an increased risk of hypoglycaemia for the subject.

BMI limits of \geq 20 kg/m² and < 40 kg/m² are chosen to include as broad a population as possible while excluding under-weight individuals in risk of unsafe weight loss, and excluding morbidly obese individuals who may be extremely insulin resistant.

Protocol Trial ID: NN9068-4229 UTN: U1111-1168-9343

EudraCT No.: 2015-001596-48

CONFIDENTIAL

Date: Version: Status: Page:

20 November 2015 | Novo Nordisk Final 29 of 107

7 **Milestones**

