Pre-trial OAD treatments must include SGLT2i either as monotherapy, or in combination with metformin ± DPP4i ± pioglitazone. If a subject is treated with DPP4i these have to be discontinued at randomisation. There will not be applied any stratification on baseline characteristics.

CONFIDENTIAL

Date: Version: Status: Page:

20 November 2015 | Novo Nordisk Final

51 of 107

2.0

Adverse events, technical complaints and pregnancies

12.1 **Definitions**

Adverse event

An adverse event (AE) is any untoward medical occurrence in a subject administered a product, and which does not necessarily have a causal relationship with this treatment. An AE can therefore be any unfavourable and unintended sign (including an abnormal laboratory finding), symptom or disease temporally associated with the use of a product, whether or not considered related to the product.

An AE includes:

- A clinically significant worsening of a concomitant illness
- A clinical laboratory adverse event: a clinical laboratory abnormality which is clinically significant, i.e. an abnormality that suggests a disease and/or organ toxicity and is of a severity that requires active management. Active management includes active treatment or further investigations, for example change of medicine dose or more frequent follow-up due to the abnormality

The following should **not** be reported as AEs:

- Pre-existing conditions, including those found as a result of screening procedures (pre-existing conditions should be reported as medical history or concomitant illness)
- Pre-planned procedures unless the condition for which the procedure was planned has worsened from the first trial related activity after the subject has signed the informed consent
- Non-serious hypoglycaemia is an AE, but is reported on a hypoglycaemic episode form instead of on an AE form, see section 8.5.2

The following three definitions are used when assessing an AE:

Severity

- o Mild no or transient symptoms, no interference with the subject's daily activities
- Moderate marked symptoms, moderate interference with the subject's daily activities
- o Severe considerable interference with the subject's daily activities; unacceptable

Causality

Relationship between an AE and the relevant trial product(s):

- o **Probable** Good reason and sufficient documentation to assume a causal relationship
- o **Possible** A causal relationship is conceivable and cannot be dismissed

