Date: Version: Status: Page:

20 November 2015 | Novo Nordisk 2.0 Final 70 of 107

treating individual subjects with T2DM. For the confirmatory secondary endpoints de jure estimands addressing efficacy are chosen as secondary estimand too.

Only endpoints derived after 26 weeks will be analysed statistically. The expected percentage of missing data is around 15%. In accordance with guidance $\frac{29}{2}$ endpoints will be assessed at frequent visits and also on subjects who prematurely discontinue treatment. If an assessment has been made both at screening and randomisation, and if not otherwise specified, the value from the randomisation visit will be used as the baseline value. If the value measured at the randomisation visit is missing and the assessment also has been made at screening, then the screening value will be used as the baseline value.

Laboratory values below the lower limit of quantification (LLOQ) will be set to ½LLOQ.

The test strategy is hierarchical testing in order to control the familywise Type I error. Inferences will be based on the primary analyses of the primary estimands. The trial will be powered with respect to the primary objective and endpoint.

Presentation of results from a statistical analysis will include the estimated mean treatment effects using LSMean for absolute values, and change from baseline where applicable. The LSMean is either obtained by Rubin's rule weighing together LSMeans from multiple imputation estimations or obtained directly from estimation of a parameterized statistical model. In addition, estimated mean treatment difference (or ratio) will be presented together with the two-sided 95% confidence interval and corresponding two-sided *p*-value.

In the statistical models explanatory factors will be parameterized as follows:

- Treatment: IDegLira, IGlar
- Pre-trial OAD: SGLT2i ± pioglitazone(pio), SGLT2i + metformin(met) ± pio, SGLT2i + $DPP4i \pm pio$, $SGLT2i + met + DPP4i \pm pio$
- Region: Europe (Finland, Hungary, Russia, Slovakia, Slovenia, Spain, Switzerland), North America (CA, USA), South America (Argentina), Asia (India)
- Visit: Planned visits for actual endpoint according flow-chart

The impact of protocol deviations and outliers may be investigated further in sensitivity analyses if deemed relevant.

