Considering inferior efficacy retention for IDegLira as opposed to IGlar amongst the anticipated 15% of subjects discontinuing randomised treatment, the expected treatment difference may be adjusted by the NI margin for discontinued subjects leading to an adjusted treatment difference of $0.85 \times 0.0\% + 0.15 \times 0.3\% = 0.045\%$. A total of 208 subjects per treatment arm will then yield a power of at least 74% (see Table 17–1)

CONFIDENTIAL

Trial ID: NN9068-4229 UTN: U1111-1168-9343 EudraCT No.: 2015-001596-48 Version: Status: Page: 2.0 Final 72 of 107

Table 17–1 Power for various rates of discontinuation

	Adjusted treatment difference (% discontinued)						
SD	0.000 (0%)	0.045 (15%)	0.060 (20%)	0.075 (25%)			
0.9	0.924	0.822	0.774	0.720			
1.0	0.863	0.737	0.685	0.629			
1.1	0.792	0.655	0.603	0.548			
1.2	0.720	0.580	0.530	0.479			

Power is computed under the assumption of 208 subjects in either arm, 1:1 randomization, and a penalty of the NI margin 0.3% in treatment difference for discontinuing subjects. SD: standard deviation.

For the confirmatory secondary endpoints body weight and hypoglycaemic episodes the marginal powers are in the order of 75% and 60% respectively under assumptions of moderate treatment effects: a treatment difference of 1 kg in weight change in favour of IDegLira, and a hypoglycaemic episode event rate of 1.8 event/PYE and rate ratio of 0.66 versus comparator. Such treatment differences have been observed for IDegLira in the phase 3a development programme. The order of hypotheses in the hierarchical testing procedure reflects this.

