- In the fourth step, for each of the 1000 copies of the dataset, missing HbA_{1c} values at the second planned HbA_{1c} measurement visit after randomisation (V14) are imputed in the same way as in the previous step, now based on an ANOVA model with pre-trial OAD and region as factors, and the HbA_{1c} values at baseline and at previous planned HbA_{1c} measurement visits as covariates, fitted to the control group (IGlar) and subjects with retrieved (V32A) data in the investigational group (IDegLira)
- This fourth step is then repeated sequentially over visits where HbA_{1c} measurement is planned, adding one visit in each step until the last planned visit (V32)
- In the sixth step a penalty equal to the non-inferiority margin 0.3% is added to the EOT HbA_{1c} value for any prematurely discontinued subject in the investigational group (IDegLira), irrespective of the EOT value being retrieved (V32A) data or an imputed value from the sequential imputation steps (step 3 to 5)

• In the seventh step, for each of the 1000 complete data sets, the change from baseline to the EOT visit (V32) is analysed using an ANOVA model with treatment, pre-trial OAD and region as factors and baseline HbA_{1c} value as a covariate

• In the eighth step, the estimates and standard errors for the 1000 data sets are pooled to one estimate and associated standard error using Rubin's rule³⁷. From these pooled estimates the confidence interval for the treatment difference and the associated *p*-value are calculated

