17.4.1.1 Primary statistical analyses primary estimand

Body weight

Let D_W be the mean treatment difference (IDegLira – IGlar) in change from baseline in body weight. The null-hypothesis of IDegLira not superior will be tested against the alternative hypothesis of superiority as given by

$$H_0$$
: $D_W \ge 0$ kg against H_A : $D_W < 0$ kg.

Superiority will be considered confirmed if the test procedure was not stopped and if the upper bound of the two-sided 95% confidence interval for D_W (mean treatment difference in change from baseline in weight) is strictly below 0 kg. This is equivalent to using a one-sided test of size 2.5%, i.e. the Type I error rate is controlled at 2.5% one-sided. The change from baseline in body weight after 26 weeks will be analysed with the J2R pattern mixture model for HbA_{1c} , substituting body weight for HbA_{1c} and leaving out the non-inferiority penalty (step 6).

Treatment-emergent hypoglycaemic episodes

Let RR be the rate ratio (IDegLira/IGlar) of the rate of treatment-emergent severe or BG confirmed symptomatic hypoglycaemic episodes during 26 weeks. The null-hypothesis of IDegLira not superior will be tested against the alternative hypothesis of superiority as given by

$$H_0$$
: $RR \ge 1$ against H_A : $RR < 1$.

Superiority will be considered confirmed if the test procedure was not stopped and if the upper bound of the two-sided 95% confidence interval for RR (rate ratio of rate of treatment-emergent severe or BG confirmed symptomatic hypoglycaemic episodes during-treatment) is strictly below 1. This is equivalent to using a one-sided test of size 2.5%, i.e. the Type I error rate is controlled at

Protocol		Date:	20 November 2015	Novo Nordisk
Trial ID: NN9068-4229		Version:	2.0	
UTN: U1111-1168-9343	CONFIDENTIAL	Status:	Final	
EudraCT No.: 2015-001596-48		Page:	78 of 107	

2.5% one-sided. The number of hypoglycaemic episodes will be analysed using a multiple imputation technique for count data under the J2R principle as follows.

For prematurely discontinued subjects the number of events in the missing period (time of premature discontinuation to planned TE period [max of 27 weeks and longest TE exposure time observed in the trial]) will be imputed using a multiple imputation technique³⁸, and assuming that all subjects have an event rate in the period before and after premature discontinuation corresponding to the event rate in the control group (IGlar). This will be done as follows:

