- As a first step, a Bayes negative binomial model is fitted to the event rate data to obtain the posterior distribution of model parameters
- In the second step, based on the estimated parameters for comparator (IGlar) in this model, the number of events in the missing period is imputed for all prematurely discontinued subjects. I.e. pre and post discontinuation event rates in the conditional distribution used for imputation are as for comparator (IGlar). Multiple copies (1000 copies) of a complete data set are generated by sampling from the estimated distribution
- In the third step, for each of the complete data sets, the number of events is analysed using a negative binomial model
- In the fourth step, the estimates and standard deviations for the 1000 data sets are pooled to one estimate and associated standard deviation using Rubin's rule³⁷. From these pooled estimates the confidence interval for the treatment ratio and the associated p-value are calculated

The negative binomial model will have a log-link function, and the logarithm of the time period, in which a hypoglycaemic episode is considered treatment-emergent, will be used as offset. The model will include treatment, pre-trial OAD and region as factors.

Glycaemic control

As above, let D be the mean treatment difference (IDegLira – IGlar) in change from baseline in HbA_{1c} . The null-hypothesis of IDegLira not superior will be tested against the alternative hypothesis of superiority as given by

$$H_0: D \ge 0\%$$
 against $H_A: D < 0\%$.

Superiority will be considered confirmed if the test procedure was not stopped and if the upper bound of the two-sided 95% confidence interval for D (mean treatment difference in change from baseline in HbA_{1c}) is strictly below 0%. This is equivalent to using a one-sided test of size 2.5%, i.e. the Type I error rate is controlled at 2.5% one-sided. The change from baseline in HbA_{1c} after 26 weeks will be analysed with the J2R pattern mixture model for HbA_{1c} but leaving out the non-inferiority penalty (step 6).

CONFIDENTIAL

Date: Version: Status: Page:

20 November 2015 | Novo Nordisk 2.0 Final 79 of 107

Insulin dose

Let D_D be the mean treatment difference (IDegLira – IGlar) in insulin dose after 26 weeks. The null-hypothesis of IDegLira not superior will be tested against the alternative hypothesis of superiority as given by

$$H_0: D_D \ge 0 U$$
 against $H_A: D_D < 0 U$.

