Superiority will be considered confirmed if the test procedure was not stopped and if the upper bound of the two-sided 95% confidence interval for D_D (mean treatment difference in insulin dose after 26 weeks) is strictly below 0 U. This is equivalent to using a one-sided test of size 2.5%, i.e. the Type I error rate is controlled at 2.5% one-sided. The insulin dose after 26 weeks will be analysed with the J2R pattern mixture model for HbA_{1c}, substituting insulin dose for HbA_{1c}, leaving out the non-inferiority penalty (step 6) and using baseline HbA_{1c} as covariate as there is no baseline dose. That is, in the sequential ANOVAs (step 3 to 5) both insulin dose at previous visits and baseline HbA_{1c} will be included as covariates whilst in the EOT ANOVA (step 7) only baseline HbA_{1c} will be included as covariate.

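### The hypoglycaemia model is the only confirmatory model without a continuous baseline covariate; adding baseline HbA1c would be a small, nearly free gain

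*Protocol*

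**What the plan says.** Section 17.4.1.1 analyses the number of hypoglycaemic episodes with a negative binomial model with log link and the logarithm of the treatment-emergent time as offset. Its terms are stated in full: "The model will include treatment, pre-trial OAD and region as factors". The imputation is built on a Bayes negative binomial model for the same event data.

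The other confirmatory models carry a continuous baseline value:

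- **HbA1c** (section 17.3.1, reused for superiority without the penalty): "ANOVA model with treatment, pre-trial OAD and region as factors and baseline HbA_{1c} value as a covariate".
- **Body weight** (section 17.4.1.1): the HbA1c model with body weight substituted, hence baseline weight as covariate.
- **Insulin dose** (section 17.4.1.1): the HbA1c model "using baseline HbA_{1c} as covariate as there is no baseline dose".

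Protocol Amendment 2 relabels the count analyses as methods 1 and 2 and leaves the model terms alone. Section 11 says of the allocation: "There will not be applied any stratification on baseline characteristics". For body weight and hypoglycaemia, section 17.1 says that "the marginal powers are in the order of 75% and 60% respectively". In section 17.4.1 hypoglycaemia is second in the superiority hierarchy, after weight and before HbA1c superiority and insulin dose.

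**The concern.** The protocol's own reasoning is applied unevenly. Insulin dose has no pre-treatment value, so its model takes baseline HbA1c instead. Hypoglycaemia counts are in the same position, because section 12.2 has no episodes recorded before trial drug is given, yet their model takes nothing and no reason is given.

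Three features make this worth a line in the review. Allocation is unstratified, so a chance difference in baseline HbA1c can be corrected only in the model. The test has the lower of the two secondary powers the protocol states, and failing it stops the hierarchy before HbA1c superiority and insulin dose. Missing counts after discontinuation are imputed from the same model, so apart from a subject's own observed count and time they depend only on the IGlar rate, OAD group and region, whereas the HbA1c imputation uses the baseline value.

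At stake is a little precision and some protection against an unlucky allocation, not validity.

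**Working it through.** **Inputs from the protocol.** 208 per arm; one-sided 2.5%; rate ratio 0.66; 1.8 events per patient-year (the arm is not clear); 26 weeks, i.e. 0.5 year; stated power about 60%.

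**Assumed, because not given.** Dispersion k (solved for below); baseline HbA1c SD 1.0 (the 1.0 in section 17.1 is the planning SD of the primary endpoint, not of baseline); rate factor f of 0.9, 0.8 or 0.7 per 1% higher baseline HbA1c.

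**1. The stated 60%.** It cannot be reproduced without a dispersion, so solve for one. Var(log RR) = [1/m1 + 1/m0 + 2k]/n. Taking 1.8 as the IGlar rate, m0 = 0.9 and m1 = 0.9 × 0.66 = 0.594. Power of 60% needs SE = 0.4155/(1.960 + 0.2533) = 0.1877. Then 208 × 0.1877² = 7.33, less 1/0.594 = 1.684 and 1/0.9 = 1.111, leaves 2k = 4.54, so k is about 2.27. Across both readings of the 1.8, n of 177 or 208, and 26 or 27 weeks, k runs from about 1.7 to 2.8.

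**2. Gain from the covariate.** With b = ln f and SD 1.0, the dispersion left after adjustment is kc = (1 + 2.268)/exp(b²) − 1. A subject with standardised baseline x has mean μ = m·exp(bx − b²/2) and contributes information μ/(1 + kc·μ). This is averaged over a normal x, and the information matrix for treatment and covariate is inverted. Power is Φ(0.4155/SE − 1.960).

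| f per 1% | kc | SE | Power |
|---|---|---|---|
| no covariate | 2.268 | 0.1877 | 60.0% |
| 0.9 | 2.232 | 0.1871 | 60.3% |
| 0.8 | 2.109 | 0.1847 | 61.4% |
| 0.7 | 1.878 | 0.1802 | 63.5% |

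If 1.8 is the IDegLira rate (m1 = 0.9, m0 = 1.364, k = 2.743), the same calculation gives 60.4%, 61.8% and 64.5%. A simulation of 500 trials per setting (IGlar mean 0.9, marginal dispersion 2.27) gave power without and with the covariate of 60.6/59.6, 60.6/62.0 and 59.6/61.4%. Each figure has a Monte Carlo SE of √(0.6 × 0.4/500) = 2.2 points, so this agrees with a small gain and cannot resolve it.

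For scale, reaching 80% would require about 50 to 68% of the overdispersion to be removed. At f = 0.7 the covariate removes 1 − 1.878/2.268 = 17%.

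**3. Chance imbalance.** The SE of the difference in mean baseline HbA1c is 1.0 × √(2/208) = 0.098, so a difference of 0.2% is about 2 SE; one at least that large, in either direction, arises in about 4% of trials. It multiplies the rate ratio from the planned model by f^0.2 or its inverse:

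| f per 1% | f^0.2 | Shift in SE of log RR | Chance of success, given imbalance against / for IDegLira |
|---|---|---|---|
| 0.9 | 0.979 | 0.11 | 56% / 64% |
| 0.8 | 0.956 | 0.24 | 51% / 69% |
| 0.7 | 0.931 | 0.38 | 45% / 74% |

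The shift is 0.2 × |ln f|/0.1877; the last column is Φ(0.2533 ∓ shift).

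**The case against.** The best reply is that this is a preference. The model is prespecified and clear, nothing in the protocol contradicts it, and omitting a prognostic covariate from a randomised comparison leaves the test valid. Chance imbalance is ordinary sampling error, and the confidence interval already covers it because between-subject variation enters the dispersion. The asymmetry also has a plain origin: insulin dose is run through the HbA1c model, which has a baseline slot to fill, whereas the count model is a separate class. All of this stands, and it limits the point to a suggestion. It does not show that the omission is preferable.

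A reader might infer more than the documents support, in three ways:

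- *That the test is unadjusted.* It is adjusted for pre-trial OAD and region; only a continuous baseline covariate is absent.
- *That it is the weakest test in the hierarchy.* Only two secondary powers are stated, and 60% is the lower of them. None is given for HbA1c superiority or insulin dose. At the planning difference of 0.0%, HbA1c superiority has 2.5% power; it reaches 60% only at a true difference of about (1.960 + 0.2533) × √(2/208) = 0.22% in favour of IDegLira (SD 1.0).
- *That the protocol itself treats baseline HbA1c as a predictor of hypoglycaemia.* Section 6.8 says the entry range was chosen to find subjects needing intensification "without imposing an increased risk of hypoglycaemia for the subject". That justifies eligibility limits. It states no risk gradient within 7.0 to 11.0%, and both arms are titrated to the same fasting target.

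**Conclusion.** The point holds as a minor improvement. The hypoglycaemia model is the one confirmatory model without a continuous baseline covariate, and the reason the protocol gives for borrowing baseline HbA1c in the insulin dose model applies equally to counts. There is no bias on average and no type I error inflation.

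Under the assumed baseline SD of 1.0 and rate factors of 0.9 to 0.7 per 1%, the power gain is about 0 to 4 points (4.5 at the extreme of the second reading of the 1.8). It is nil if baseline HbA1c does not predict the count. Adjustment therefore does not cure the 60% power. Its clearer use is in the occasional trial with a marked baseline imbalance, where it removes a shift of roughly 0.1 to 0.4 SE. With a log link and randomised arms, the target rate ratio is unchanged by the covariate.

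**What to change.** Prespecify baseline HbA1c as a covariate in the negative binomial model of section 17.4.1.1, in both the Bayes imputation step and the analysis step. Carry it through methods 1 and 2 and the nocturnal analysis in section 17.4.2.2. The method 1 tipping point analysis and the secondary-estimand analysis in section 17.4.1.3 reuse this model and would follow. Alternatively, add a sentence saying why the covariate is left out.

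The cost is one extra model parameter and a short text change, made before database lock. No data are added: HbA1c is required for eligibility, and if the randomisation value is missing, section 17 provides that "then the screening value will be used as the baseline value".

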17.1 Sample size calculation

The sample size is based on the primary objective and primary endpoint of the trial.

The primary objective of this trial is to confirm the effect of IDegLira in terms of glycaemic control in subjects with T2DM on previous treatment with SGLT2i ± OAD therapy. This will be done by

Protocol
Trial ID: NN9068-4229
UTN: U1111-1168-9343
EudraCT No.: 2015-001596-48

CONFIDENTIAL

Date: Version: Status: Page:

20 November 2015 | Novo Nordisk 2.0 Final 71 of 107

comparing the difference in change from baseline in HbA_{1c} after 26 weeks to a non-inferiority margin of 0.3% for IDegLira versus IGlar, both arms on continued SGLT2i ± OAD therapy.

The non-inferiority margin of 0.3% is due to guidance $\frac{30,31}{2}$, a treatment effect -0.85% $[-1.04; -0.66]_{95\% \text{ CI}}$ of IGlar versus placebo reported in a placebo controlled clinical trial in T2DM subjects, and the effect of IGlar stated to be clinically equal to NPH³³. With the superiority of IGlar to placebo and IGlar established as being as efficacious as NPH, a non-inferiority margin of 0.3% is considered to give sufficient assay sensitivity in this trial.

Formally, let D be the mean treatment difference (IDegLira – IGlar) in change from baseline in HbA_{1c}. The null-hypothesis of IDegLira inferior by 0.3% or more will be tested against the alternative hypothesis of non-inferiority (IDegLira inferior by less than 0.3%) as given by

$$H_0: D \ge 0.3\%$$
 against $H_A: D < 0.3\%$.

Non-inferiority will be considered confirmed if the upper bound of the two-sided 95% confidence interval for D (mean treatment difference in change from baseline in HbA_{1c}) is strictly below 0.3%. This is equivalent to using a one-sided test of size 2.5%, i.e. the Type I error rate is controlled at 2.5% one-sided.

Accordingly, the sample size is calculated using a t-statistic under the assumptions of a one-sided test of size 2.5%, a mean treatment difference of 0.0%, a standard deviation of 1.0%, a noninferiority margin of 0.3%, and that 15% of the randomised subjects will be excluded from the PP analysis set. These assumptions are based on experience from the phase 3a development programs for IDegLira and insulin degludec. With the 1:1 randomisation scheme the sample size is set to 208 subjects per treatment arm; in total 416 subjects will be randomised. This will ensure a nominal power of 80% for confirming the primary objective based on PP.

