17.4.2.1 Efficacy endpoints

HbA_{1c} responder after 26 weeks (yes/no)

Two dichotomous endpoints (responder=yes/non-responder=no) will be defined based on whether a subject has met a specific target level after 26 weeks:

- $HbA_{1c} < 7.0 \%$
- $HbA_{1c} \le 6.5 \%$

Analysis of each the two responder endpoints will be based on a logistic regression model with treatment, pre-trial OAD and region as fixed factors and baseline HbA_{1c} value as a covariate, hereafter referred to as the standard logistic regression model.

For each of the multiple copies (1000) of the full dataset of the primary analysis of the primary estimand (multiple imputation J2R with retrieved data, NI penalty section 17.3.1) the responder endpoints are derived without using the non-inferiority penalty (step 6) and analysed with the standard logistic regression model. Estimates are pooled using Rubin's rule.

Protocol
Trial ID: NN9068-4229
UTN: U1111-1168-9343

Date: 20 November 2015 | Novo Nordisk
Version: 2.0
Status: Final

Page:

81 of 107

HbA_{1c} responder endpoints without weight gain after 26 weeks

EudraCT No.: 2015-001596-48

Responder for HbA_{1c} without weight gain after 26 weeks will be defined as

- HbA_{1c} < 7.0% and change in body weight from baseline ≤ 0 kg
- HbA_{1c} \leq 6.5% and change in body weight from baseline \leq 0 kg

Theses endpoint will be analysed as the HbA_{1c} responder endpoints, now using also the multiple copies of the full dataset for weight (section $\underline{17.4.1}$), and including baseline weight too as covariate in the standard logistic regression model.

HbA_{1c} responder endpoints without treatment-emergent severe or BG confirmed symptomatic hypoglycaemic episodes after 26 weeks

Responder for HbA_{1c} without treatment-emergent severe or BG confirmed symptomatic hypoglycaemic episodes after 26 weeks will be defined as

- HbA_{1c} < 7.0% and without treatment-emergent severe or BG confirmed symptomatic hypoglycaemic episodes during the last 12 weeks of treatment
- HbA_{1c} \leq 6.5% and without treatment-emergent severe or BG confirmed symptomatic hypoglycaemic episodes during the last 12 weeks of treatment

Theses endpoints will be analysed as the HbA_{1c} responder endpoints, where subjects with less than 12 weeks of treatment conservatively will be set to being non-responder.

HbA_{1c} responder endpoints without treatment-emergent severe or BG confirmed symptomatic hypoglycaemic episodes and weight gain after 26 weeks

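### The confirmatory insulin dose analysis leaves out baseline body weight, which is already collected and would probably narrow the confidence interval at almost no cost

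*Protocol*

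**What the plan says.** Insulin dose after 26 weeks, in units per day, is the fourth and last superiority test in the hierarchy of section 17.4.1. Section 17.4.1.1 takes over the HbA1c multiple imputation model without the penalty step and uses baseline HbA1c "as covariate as there is no baseline dose". Three things follow from that text and from the steps in 17.3.1:

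- **Sequential imputation (steps 3 to 5):** pre-trial OAD, region, baseline HbA1c and doses at earlier visits.
- **Final model (step 7):** treatment, pre-trial OAD, region and baseline HbA1c.
- **MMRM for the secondary estimand (17.4.1.3):** again baseline HbA1c as the covariate for dose.

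Amendment 2 (section 2.21) renames the imputation approach and keeps the covariate. The test is at the usual level: "the Type I error rate is controlled at 2.5% one-sided".

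Body weight is measured at V2 in every subject, fasting (flow chart; section 8.4.1). It appears in none of the insulin dose models.

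**The concern.** The absence of a baseline dose explains why the outcome's own baseline value cannot be used. It does not explain why another collected baseline value is left out. HbA1c and body weight, the other continuous confirmatory endpoints, are each adjusted for their own baseline; dose is not, so it has more to gain from a further predictor.

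Weight is a reasonable candidate. The endpoint is in U rather than U/kg, and eligible BMI runs from 20 to about 40 kg/m², a twofold range of weight at a given height. All subjects start at 10 units or dose steps and are titrated to the same pre-breakfast target, so the dose reached should reflect individual need, at least in the uncapped IGlar arm.

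Two things are at stake: the precision of a confirmatory estimate, and the realism of some imputed doses. Under step 1, an IDegLira subject who stops treatment and has no V32A data loses all post-randomisation values. The imputed dose then rests only on pre-trial OAD, region and baseline HbA1c. Body size does not enter even indirectly, because no observed earlier dose remains.

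**Working it through.** **1. The plan's own figure.** No effect, SD or power is stated for insulin dose, so the only figure to reproduce is the trial size. Section 17.1 assumes "a mean treatment difference of 0.0%, a standard deviation of 1.0"%, "a non-inferiority margin of 0.3"%, a one-sided 2.5% test, 80% power and that "15% of the randomised subjects will be excluded from the PP analysis set". The t-based calculation needs 176 per arm, and 176 / 0.85 = 207.06, rounded up to 208. This agrees with the plan: "With the 1:1 randomisation scheme the sample size is set to 208 subjects per treatment arm". Table 17–1 also reproduces in all 16 cells. None of these figures depends on the insulin dose covariate; they supply only n = 208 per arm.

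**2. Effect of adding weight on the standard error.** Let rho be the partial correlation of V2 weight with week 26 dose, given treatment, pre-trial OAD, region and baseline HbA1c. The documents give no value, so rho is an assumption. The standard error is multiplied by √(1 − rho²), and the equivalent sample size per arm is 208 / (1 − rho²).

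| rho (assumed) | SE multiplier | Equivalent n per arm |
|---|---|---|
| 0.1 | 0.995 | 210 |
| 0.2 | 0.980 | 217 |
| 0.3 | 0.954 | 229 |
| 0.4 | 0.917 | 248 |
| 0.5 | 0.866 | 277 |

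**3. Cost.** Step 7 now has 9 parameters: intercept 1, treatment 1, pre-trial OAD 3, region 3, HbA1c 1. Weight makes 10. Residual degrees of freedom fall from 416 − 9 = 407 to 416 − 10 = 406, which raises the SE by √(407/406) = 1.0012, about 0.1%. Break-even is at rho = √(1/407) = 0.05; above that, adjustment gains.

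**4. Effect on power.** This needs a standardised dose difference, also assumed. Noncentral t, 208 per arm, one-sided 2.5%:

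| Standardised difference (assumed) | Without weight | rho 0.3 | rho 0.5 |
|---|---|---|---|
| 0.25 | 72.0% | 76.0% | 83.6% |
| 0.40 | 98.3% | 98.9% | 99.7% |
| 0.50 | 99.9% or more | 99.9% or more | 99.9% or more |

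**5. A scenario with the dose cap.** Assume weight 88 (SD 18) kg, a need of 0.55 U/kg with log-SD 0.35, 0.45 or 0.60, the 50-unit cap on IDegLira, and no insulin-sparing effect. Simulation gives an efficiency gain of about 25%, 14% and 8% in equivalent subjects. Power is already 99.5% or more without weight in all three settings, because the cap alone separates the arms. All inputs except the cap and the sample size are assumptions.

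**The case against.** The strongest reply is that nothing here is wrong. The comparison is randomised, the prespecified model gives a valid estimate and test, and a chance imbalance in weight is already reflected in the confidence interval. All of that stands. A reader might infer that the analysis is biased, or that its error rate is at risk; the documents support neither.

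A reader might also infer that the model adjusts for HbA1c alone. It does not: pre-trial OAD and region are in it, and earlier doses are in the imputation models.

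Nor do the documents establish weight as the main driver of dose. The start is a fixed number of units, and each step follows SMPG, with no per-kg rule (Appendix A, section 3). The IDegLira cap would weaken any relation in that arm. Section 6.8 speaks of "excluding morbidly obese individuals who may be extremely insulin resistant", which concerns people kept out of the trial and says little about scaling within the enrolled range. Section 17.4.2.1 adds weight to a responder model ("and including baseline weight too as covariate in the standard logistic regression model"), but there weight change is part of the endpoint, so it is only a weak precedent. What survives is that final dose follows individual need, and that some association with weight is plausible but of unknown size.

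Finally, precision of the dose model is not what limits the confirmatory claim. Dose is reached only after weight, hypoglycaemia and HbA1c superiority. Section 17.1 puts hypoglycaemia at about 60% power, so under those assumptions the chance of reaching the dose test cannot exceed about 60%. This stands, and it keeps the severity low. The imputation point is also narrow: it concerns a subset of the anticipated 15% who discontinue, since V32A is meant to collect their actual dose.

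**Conclusion.** The point holds as an efficiency improvement of low severity, not as an error or contradiction. The stated reason for the covariate choice does not account for leaving out V2 weight, and the planned analysis probably gives up some precision.

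The loss cannot be derived from the documents. It is 0.5% of the standard error at an assumed partial correlation of 0.1, below 5% up to 0.3, and 13% at 0.5. A material gain in power appears only if the standardised dose difference is small, around 0.25; with a larger difference the test is close to saturated. The main benefit is therefore a narrower interval for the dose difference, with more realistic imputed doses for discontinued IDegLira subjects without V32A data as a second, smaller one.

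**What to change.** In 17.4.1.1 (Insulin dose) and 17.4.1.3, prespecify V2 fasting body weight as a covariate beside baseline HbA1c in steps 3 to 5, in step 7 and in the MMRM. Make the change in the imputation and final models together: if weight entered step 7 only, the imputed doses would carry too weak a relation to it.

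The value is already collected, so the cost is a line of text and one degree of freedom in step 7. In the MMRM, which by 17.3.2 crosses each covariate with visit, it is one per visit. Because the trial is open-label, the choice should be fixed before outcome data by arm are examined.
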